6.4 Analysis of Efficacy

6.4.1 Analysis of Primary Efficacy Endpoint(s)

The primary efficacy endpoint is change from baseline to week 24 in distance walked on the 6MWT.

6.4.1.1 Primary Analysis for Primary Efficacy Endpoint

Analysis population: FAS, Analysis group: ASP0367 30 mg group, ASP0367 75 mg group or placebo group

The primary efficacy endpoint will be analyzed on FAS for primary analysis. In order to compare the change from baseline in distance walked on the 6MWT between ASP0367 and placebo group, the null and alternative hypothesis will be constructed:

H₀: The change from baseline in distance walked on the 6MWT at week 24 for each dose of ASP0367 and placebo are the same.

H₁: The change from baseline in distance walked on the 6MWT at week 24 for each dose of ASP0367 and placebo are not the same.

To control the family-wise type I error rate (i.e., the probability of incorrectly rejecting at least one true null hypothesis), the hierarchical testing procedure in the following order will be applied:

Comparison between ASP0367 75 mg and placebo Comparison between ASP0367 30 mg and placebo

Comparison to placebo will be conducted using a MMRM with treatment group (3 level: ASP0367 75 mg, ASP0367 30 mg, and placebo group), week (weeks 4, 12 and 24) as factors, with baseline measurement as a covariate, as well as an interaction of treatment by week and an interaction of baseline measurement by week. An unstructured covariance structure will be used to model the within-participant correlation. If the unstructured covariance structure fails to converge, then compound symmetry will be used. The Kenward-Roger approximation will be used to estimate denominator degrees of freedom and adjust standard errors.

Contrasts will be constructed to compare each dose group of ASP0367 to the placebo group at week 24. The LS mean change from baseline in distance walked on the 6MWT with associated SE will be displayed for each treatment group. Estimated treatment differences between each dose group of ASP0367 and placebo group along with corresponding 2-sided 90% CI and p-values will also be presented.

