3 SAMPLE SIZE

The sample size of this study was determined from feasibility and statistical perspectives. From the statistical perspective, 57 participants (19 participants in each group) will provide > 80% power to detect a difference of 45 meters in 6MWT between ASP0367 and placebo at a 2-sided significance level of 0.10 assuming a common standard deviation of 55.0 meters.

The 45-meter difference in 6MWT under the 24-week treatment is assumed based on preliminary results that were observed in cohort 1 of the MMPOWER-2 phase 2 randomized controlled crossover study of elamipretide [Cohen et al, 2018].

Considering the interim analysis, 60 participants will be required to maintain > 80% power in the efficacy analysis, and assuming an approximately 10% study discontinuation (drop out) rate during the double-blind treatment period, 66 participants are required to be randomized. This sample size supports an evaluation of proof of concept.

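### If the unstructured MMRM does not converge, the SAP's only fallback is compound symmetry, which gives a wrong week-24 standard error whenever visit variances differ

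*SAP*

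**What the plan says.** SAP 6.4.1.1 specifies the covariance for the primary MMRM: "An unstructured covariance structure will be used to model the within-participant correlation". The next sentence gives the single fallback: "If the unstructured covariance structure fails to converge, then compound symmetry will be used". Inference is model-based: "The Kenward-Roger approximation will be used to estimate denominator degrees of freedom and adjust standard errors". No structure between the two is listed, and no empirical (sandwich) SE is named.

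The model has "week (weeks 4, 12 and 24) as factors, with baseline measurement as a covariate". It also lets both the treatment effect and the baseline slope differ from week to week. The target is one visit: "Contrasts will be constructed to compare each dose group of ASP0367 to the placebo group at week 24". Results are reported as LS means with SEs, treatment differences, 90% confidence intervals and p-values.

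SAP 6.4.2 applies the same model to 5XSTS, MFIS and the two Neuro-QoL T-scores, so they inherit the fallback. Protocol 9.4.2.1 names no covariance structure, so nothing there overrides the SAP. The only SD in either document is in SAP section 3 and protocol 9.2: "assuming a common standard deviation of 55.0 meters". It is common to the arms, and no value by visit is given.

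**The concern.** Compound symmetry has two parameters: one variance for all three visits and one correlation for all pairs of visits. The unstructured matrix has six. Falling back from six to two drops the visit-specific variances, which are what a single-visit contrast depends on. The week-24 contrast is then judged against a variance pooled over weeks 4, 12 and 24.

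If the week-24 variance is above that pool, the reported SE is too small, the test is anti-conservative and the interval too narrow. If it is below, the SE is too large and the interval too wide. Kenward-Roger allows for covariance parameters having been estimated. It takes the chosen form as correct.

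Since the trial met its futility criterion (SAP 6.7.1), the stake is mainly the interval. Readers of a stopped trial use the 90% limits to judge which effects are excluded, including the 45 m used for sample size.

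**Working it through.** **Inputs.** Two-sided level 0.10, difference 45 m, SD 55.0 m and 19 per group come from SAP section 3. The three visits, both by-week interactions and the week-24 contrast come from SAP 6.4.1.1. The interim used 33 participants (SAP 6.7.1); 11 per arm assumes an equal split. SDs by visit are assumptions. In the scenarios with constant or growing variance, week 24 is held at 55 m.

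**The plan's own figure.** SE = 55 × √(2/19) = 17.84 m. Power ≈ Φ(45/17.84 − 1.645) = Φ(0.877) = 0.810, so the stated power above 80% reproduces by the normal approximation. A two-sample t calculation gives 0.796, and a t with three-arm pooled degrees of freedom gives 0.801. The sample size is not affected by this point.

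**SE under compound symmetry.** With complete data and both by-week interactions, the week-24 estimate is the same under any covariance. Only its SE changes. Compound symmetry uses the mean of the visit variances, so

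- r = SE(compound symmetry) / true SE = √[(v4 + v12 + v24) / (3 × v24)]
- actual two-sided error = 2 × [1 − Φ(1.645 × r)]

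Example, 45/50/55 m: (2025 + 2500 + 3025)/3 = 2516.7; r = √(2516.7/3025) = 0.912; error = 2 × [1 − Φ(1.500)] = 13.4%.

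The last two columns are for 11 per arm, with true SE = week-24 SD × √(2/11).

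| Assumed SD, weeks 4/12/24 (m) | r | Actual error | 90% CI coverage | True SE (m) | Reported SE (m) |
|---|---|---|---|---|---|
| 55/55/55 | 1.000 | 10.0% | 90.0% | 23.5 | 23.5 |
| 50/52.5/55 | 0.955 | 11.6% | 88.4% | 23.5 | 22.4 |
| 45/50/55 | 0.912 | 13.4% | 86.6% | 23.5 | 21.4 |
| 35/45/55 | 0.832 | 17.1% | 82.9% | 23.5 | 19.5 |
| 55/45/35 | 1.307 | 3.2% | 96.8% | 14.9 | 19.5 |

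**Effect on the interval.** At 11 per arm and a week-24 SD of 55 m, the correct 90% half-width is about 1.645 × 23.5 = 38.6 m. Compound symmetry would report 1.645 × 21.4 = 35.2 m for 45/50/55, or 1.645 × 19.5 = 32.1 m for 35/45/55. A correct interval excludes 45 m only if the estimate is below 45 − 38.6 = 6.4 m. Under 35/45/55 the reported interval would exclude it for any estimate below 45 − 32.1 = 12.9 m.

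**Simulation check.** REML fits were simulated under the null with three arms of 11, 10% dropout, correlation about 0.6 and 1500 runs per scenario. A t reference with approximate degrees of freedom was used, not full Kenward-Roger.

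| SDs (m) | Compound symmetry: model SE / empirical SE | Rejection, compound symmetry | Rejection, unstructured |
|---|---|---|---|
| 55/55/55 | 24.6 / 24.1 | 8.7% | 9.5% |
| 45/50/55 | 22.4 / 24.6 | 13.3% | 9.6% |
| 35/45/55 | 20.2 / 24.3 | 16.9% | 9.2% |

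The simulation agrees with the formula. The unstructured fit failed in 0 of 1500 runs in each scenario. That test is somewhat favourable, because those fits started from the true covariance.

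**The case against.** The strongest reply is that harm needs two things together: the unstructured fit must fail, and the visit variances must differ. The documents give no sign of either. Six covariance parameters from three visits is a small demand, and no simulated fit failed at 11 per arm. This stands, and it is why the point is minor.

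A reader might infer that week 24 is the visit with the largest variance, so that the fallback inflates the type I error. The documents do not support that. They give one SD, 55.0 m, and none by visit. With equal variances there is no bias, and with falling variances the test becomes conservative.

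A reader might also infer that the futility recommendation rested on a wrong SE. SAP 6.7.1 says the interim used the same MMRM as the primary analysis. It does not say that the unstructured fit failed or that compound symmetry was used, so this too is unsupported.

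The futility outcome makes a false positive claim a lesser worry, and SAP 6.4.2 leaves the secondary comparisons unadjusted for multiplicity, so no controlled error rate is at stake there. Both points stand. Neither protects the width of the intervals, which are still to be reported.

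Finally, the plan does pre-specify a structure, a deterministic fallback and a degrees-of-freedom method. It contains no contradiction and no wrong figure. There is simply a better fallback available at almost no cost.

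**Conclusion.** The point holds as a minor specification improvement. If the fallback is used and visit variances differ, the week-24 SE is wrong and Kenward-Roger will not correct it. With week 24 at 55 m and the growth patterns tabulated, the SE is 0% to 17% too small and the actual error is 10.0% to 17.1% at nominal 10%. With 55/45/35 it is about 31% too large.

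These sizes rest on assumed SDs by visit and on complete data. The simulation with 10% dropout agrees for the constant and growing patterns. The chance that the fallback is needed is low. The practical consequence is a mis-sized 90% interval for the 6MWT or, if the fallback is needed there, for 5XSTS, MFIS or a Neuro-QoL score. The documents do not show that any reported or interim result is affected.

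**What to change.** Replace the fallback sentence in SAP 6.4.1.1 with an ordered sequence:

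1. Unstructured.
2. Heterogeneous Toeplitz (3 variances + 2 correlations = 5 parameters).
3. Heterogeneous first-order autoregressive or heterogeneous compound symmetry (3 + 1 = 4 parameters). Name one in advance.
4. Plain compound symmetry, only if all of these fail.

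Use Kenward-Roger for steps 1 to 3. At step 4, use a small-sample-corrected sandwich SE in place of Kenward-Roger: the two are not combined, and an uncorrected sandwich can itself understate the SE at this sample size. Keep the heterogeneous structures ahead of the sandwich, because the sandwich does not repair a wrong correlation pattern when week-24 values are missing.

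State in the CSR which structure was used for each endpoint. If the SAP can no longer be amended and plain compound symmetry was used, show a heterogeneous-variance fit beside it and record the addition; SAP section 1 already sends consequential changes to the CSR.

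The cost is one SAP sentence and one line of reporting per endpoint. If the unstructured model converges, no result changes.

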6.4.2 Analysis of Secondary Efficacy Endpoints

Analysis population: FAS, Analysis group: ASP0367 30 mg group, ASP0367 75 mg group or placebo group

The change from baseline to week 24 in 5XSTS and MFIS will be analyzed using the same MMRM model as with the primary analysis for primary endpoint.

The change from baseline to week 24 in T-scores for Neuro-QoL Short Form Fatigue and Lower Extremity Function (Mobility) scores will be analyzed using the same MMRM model as with the primary analysis for primary endpoint.

For PGIC score at week 24, responder analysis will be used. Participants with scores of 1 (Very Much Improved), 2 (Much Improved) and 3 (Minimally Improved) will be considered

as responders, whereas participants with scores of 4 (No Change), 5 (Minimally Worse), 6 (Much Worse) and 7 (Very Much Worse) will be treated as nonresponders.

For PGIS score, responder analysis will be used for post baseline visits. Participants who have a lower severity score than baseline will be considered as responders, otherwise will be treated as non-responders. The participants who have 0 (None) as baseline score will be excluded from this responder analysis.

For the secondary endpoints, the multiplicity of statistical comparison will not be adjusted.

The change from baseline in 6MWT, 5XSTS, MFIS and Neuro-QoL Short Form Fatigue and Lower Extremity Function (Mobility) scores will be summarized by treatment group and time point (other than week 24).

PGIC score and PGIS score will also be summarized by treatment group and time point (other than week 24).

6.5 Analysis of Safety

Analysis population: SAF, Analysis group: 30, 75 mg of ASP0367, ASP0367 any dose group or placebo group

6.5.1 Adverse Events

AEs will be coded using the MedDRA.

An overview table will include the following:

- Number of TEAEs,
- Number and percentage of participants with TEAEs,
- Number of drug related TEAEs,
- Number and percentage of participants with drug related TEAEs,
- Number of serious TEAEs,
- Number and percentage of participants with serious TEAEs,
- Number of serious drug related TEAEs,
- Number and percentage of participants with serious drug related TEAEs,
- Number of TEAEs leading to death,
- Number and percentage of participants with TEAEs leading to death,
- Number of drug related TEAEs leading to death,
- Number and percentage of participants with drug related TEAEs leading to death,
- Number of TEAEs leading to withdrawal of study drug,
- Number and percentage of participants with TEAEs leading to withdrawal of study drug,
- Number of drug related TEAEs leading to withdrawal of study drug,
- Number and percentage of participants with drug related TEAEs leading to withdrawal of study drug, and
- Number of deaths.

Number of deaths is counted all reported deaths after starting administration of the IP. For participants who move to the OLE, all reported deaths after starting administration of the IP to moving to the OLE.

The number and percentage of participants with TEAEs, as classified by SOC, and PT will be summarized by analysis group. Summaries will be provided for the following:

- TEAEs,
- drug related TEAEs,
- serious TEAEs,
- drug related serious TEAEs,
- TEAEs leading to withdrawal of study drug,
- drug related TEAEs leading to withdrawal of study drug,
- TEAEs excluding Serious AEs that equal to or exceed a threshold of 5.0% in any analysis group.

The number of TEAEs and the number and percentage of participants with TEAEs, as classified by SOC and PT will be summarized by severity and by relationship to study drug. In the participant count, if a participant has multiple TEAEs with the same SOC or PT, but with differing severity or relationship, then the participant will be counted once with the worst severity and highest degree of relationship. If severity or relationship is missing for all episodes of the event, the participant will be counted under missing severity or relationship.

The following AESIs are defined:

- Cardiac tissue injury defined by cTnI above ULN or if the cTnT is above ULN or baseline if the participant's baseline value was above ULN and a TEAE as pre-defined by a MedDRA search strategy for elevated troponin.
- Cardiac tissue injury with any signs or symptoms defined by an echocardiogram or electrocardiogram interpretation is reported as abnormal, clinically significant and a TEAE as pre-defined by a MedDRA search strategy for cardiac complaints.
- Skeletal muscle injury defined by CK increase >= 5 times the value of the ULN or the individual's baseline value, whichever is higher and a TEAE as pre-defined by a MedDRA search strategy for skeletal muscle injury.

AESIs prior to version 9.0 of the protocol did not include elevations in cTnT in the definition of an AESI but instead only included elevations of cTnI. All participants participated in protocol version 7.0 or earlier; therefore participants for whom elevations in cTnT were observed may not have been identified as having experienced an AESIs during study conduct and for this reason may not have had additional ECG and echocardiographic evaluations performed.

The number and percentage of participants who report AESIs will be summarized by analysis group. In addition, any (serious) AEs that are considered abuse of the study drug will also be collected and followed. The number and percentage of AEs of special interest related to abuse, as classified by SOC and PT will be summarized by analysis group.

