Sequential monitoring for skeletal muscle injury will include assessment of CK, transaminases and lactate dehydrogenase at protocol-specific intervals. An individual participant may be required to discontinue treatment if they develop an elevation in CK levels \geq 5 times the value of the ULN or the individual's baseline value, whichever is higher and it is judged that this elevation is not related to an explainable increase including excessive movement, fall or disease state.

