7.3.6 Adverse Events of Special Interest

The following (S)AEs are considered of special interest:

- Cardiac tissue injury, indicated by cTnI above ULN (see Appendix 10.9 for reference range) or if the cTnT is above ULN (see Appendix 10.9 for reference range) or baseline if the participant's baseline value of cTnT was above ULN
- Cardiac tissue injury with any signs or symptoms reflecting cardiac involvement, inclusive of new onset shortness of breath confirmed by ECG or echocardiogram
- Skeletal muscle injury indicated by CK increase ≥ 5 times the value of the ULN or the individual's baseline value, whichever is higher judged not related to an explainable increase, including excessive movement, fall or disease state
- Suspected abuse of IP. ASP0367 has high-risk of doping potential and was assigned to category D (i.e., high-risk doping potential in sport). Hence, suspected abuse of IP will be analyzed for its muscle function improving characteristics per Astellas Doping Potential Guideline and will be closely followed up via compliance and participants, who will be expected to meet 100% compliance with IP. Compliance will be assessed by counting returned tablets. Deviations from the prescribed dose regimen will be recorded. When IP is administered at the study site, it will be administered under the supervision of study personnel [Section 6.4 Investigational Product Compliance]. Suspected abuse during study will be reported as special situations per [Section 7.3.7 Special Situations].

AEs (serious or nonserious) of special interest are to be collected in the CRF. If the AEs of special interest are classified as serious, they are to be collected via the SAE worksheet and reported within 24 hours as described in [Section 10.3.6 Reporting Procedures for Serious Adverse Events].

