- Participant who develops any signs or symptoms potentially reflecting cardiac involvement, inclusive of new onset shortness of breath, should interrupt IP and undergo ECG, echocardiogram, and have a cTnI drawn to be evaluated prior to continuing IP.
- Participant who develops an elevation in CK levels ≥ 5 times the value of the ULN or the individual's baseline value, whichever is higher and it has been judged that this elevation is not related to an explainable cause such as excessive activity or disease state.
- Participant who develops elevated levels of ALT or AST > 3 × ULN, or TBL > 2 × ULN persisting after 72 hours in the absence of elevated CK levels must discontinue IP. Generally, liver chemistry will be followed by repeated measurements until they return to baseline or stable values.
- Participant who presents evidence of suicidality during the C-SSRS assessments by meeting the criteria at a level of 4 or 5 since last visit must discontinue IP and upon immediate evaluation, the investigator will decide an appropriate referral.
- Participant who develops symptomatic viral infection should be evaluated by the Investigator and assessed for the need to stop IP until clinically improved.
- Participant who newly develops signs or symptoms of bulbar weakness, such as dysphagia, dysphonia, hoarseness or drooling/sialorrhea, should discontinue IP.
- Participant with a new requirement for oxygen therapy or for ventilatory support, inclusive of any respiratory device to support breathing, such as home ventilators and any form of non-invasive positive pressure ventilation (including CPAP, BiPAP, and AVAPS), should discontinue IP.

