6.5.2 Clinical Laboratory Evaluation

Quantitative values including hematology, biochemistry, and urinalysis will be summarized using mean, standard deviation, minimum, maximum and median by analysis group at each analysis visit. Additionally, a within-participant change will be calculated as the post-baseline measurement minus the baseline measurement and summarized in the same way.

Frequency tabulations of qualitative clinical laboratory variables (urinalysis) will be presented for each analysis group at each visit.

Additionally, amylase, lipase and troponin elevations above the ULN and 2xULN will be summarized by analysis group. The denominator for each criterion will be the number of participants who have at least one value after the day of first IP taken to 28 days after the last dose of IP for the double-blind treatment period of the study or moving to the OLE, whichever comes first.

The number and percentage of participants meeting the criteria during the defined period above will be summarized by analysis group.

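### Neither SAP plans a count of participants with CK at least 5 times the higher of ULN or baseline that does not also require a coded adverse event

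*SAP*

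**What the plan says.** Protocol 7.3.6 introduces its list with "The following (S)AEs are considered of special interest". The muscle entry is a CK rise of at least 5 times the reference value, "whichever is higher judged not related to an explainable increase, including excessive movement, fall or disease state". The section adds that "AEs (serious or nonserious) of special interest are to be collected in the CRF". The same multiple appears in protocol 2.3.1.3 and in 8.1 ("Participant who develops an elevation in CK levels ≥ 5 times the value of the ULN or the individual's baseline value, whichever is higher"), again with a judgement that the rise is not otherwise explained.

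Section 6.5.1 of the 52-week SAP and of the 76-week SAP keeps the CK multiple, leaves out that judgement, and adds a condition: "whichever is higher and a TEAE as pre-defined by a MedDRA search strategy for skeletal muscle injury". The troponin AESI has a matching clause: "value was above ULN and a TEAE as pre-defined by a MedDRA search strategy for elevated troponin".

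Section 6.5.2 of both SAPs then plans participant counts on laboratory values alone: "amylase, lipase and troponin elevations above the ULN and 2xULN will be summarized by analysis group". Section 6.5.2.1 does the same for liver tests and uses the baseline value where it exceeds ULN. CK appears in neither list. It is covered by summary statistics at each visit, by the laboratory listings in protocol 9.4.3.2 and, in the 76-week SAP only, by a low/normal/high class.

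**The concern.** Protocol 2.3.1.1 names heart and skeletal muscle as the target organs of toxicity, and safety relative to placebo is a primary objective. Protocol 2.3.1.3 promises that "Sequential monitoring for skeletal muscle injury will include assessment of CK, transaminases and lactate dehydrogenase at protocol-specific intervals". Yet the only planned count at the CK cut-off is one that also needs a coded adverse event.

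That condition brings in the investigator's judgement. Under protocol 7.2.1 and 10.3.1.1, a laboratory abnormality put down to the underlying disease is not treated as clinically significant, or need not be reported, unless it is worse than expected for that participant. The disease here is a myopathy, so a CK rise can readily be attributed to it. A participant who crosses the cut-off without a coded muscle event would appear in no planned participant count at that level. Amylase and lipase, for which protocol 2.3.1.2 reports no treatment or dose trend in the phase 1 data, do get such counts.

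**Working it through.** The documents state no figure on this point, so the check is a count of planned rows and a comparison of definitions.

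**Laboratory-only threshold counts in each SAP**
- Liver (6.5.2.1): ALT 6 + AST 6 + ALT or AST 6 + ALP 3 + bilirubin 1 + combinations 2 = 24.
- Amylase, lipase, troponin (6.5.2): 3 analytes × 2 cut-offs = 6.
- Total: 24 + 6 = 30. If troponin means cTnI and cTnT separately, 24 + 4 × 2 = 32.
- CK at 5 times the higher of ULN or baseline: 0.

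The totals show only which analytes are covered. The liver rows overlap, and the figures do not measure harm.

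**What the other CK output shows**
- By-visit mean, SD, median, minimum and maximum: the group maximum can show that an extreme value occurred. It does not show how many participants crossed, and it is not relative to each participant's baseline.
- Low/normal/high class (76-week SAP only): shows values above range, with no 5-times level.
- Listings: individual cases can be found, but the reader must do the counting.

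**What the adverse-event condition could do**
The share of crossings with a coded event is unknown. As an assumed example, take 4 participants crossing the cut-off. If 25%, 50% or 75% have a coded event, the AESI table shows on average 4 × 0.25 = 1, 4 × 0.50 = 2 or 4 × 0.75 = 3 of them.

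**Troponin**
Counts above ULN and above 2 × ULN already exist without an adverse-event condition. The 6.5.2 text does not say whether cTnI and cTnT are tabulated separately, and gives no rule for a raised baseline. Protocol Appendix 10.9 gives the cTnT ULN as 14.0 pg/mL, so 2 × ULN = 28.0. With assumed values:
- Baseline 20, later 18: above ULN, not above baseline.
- Baseline 20, later 26: above ULN, above baseline, not above 28.0.

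Both fall in the same row, although only the second meets the laboratory part of the cTnT AESI criterion.

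**The case against.** The case for leaving the SAPs alone has real strength.

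A reader might infer that the SAPs contradict the protocol by adding an adverse-event condition. They do not: the protocol itself frames AESIs as adverse events, and its section 9.4.3 plans no AESI table at all. Nor is 5 times alone the protocol's definition of muscle injury, since every use of it carries the judgement about explanation. The adverse-event condition partly restores that judgement.

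A reader might also infer that true muscle injury is being hidden. An unexplained rise at this level is named in 7.3.6 and is to be recorded as an AESI, so it should have an adverse-event record. What mainly escapes is a rise judged explainable. Coded events are also tabulated by term and severity whether or not they meet the AESI definition.

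For troponin, a reader might infer that laboratory-only counts are missing. They are not. cTnI and cTnT have different units and limits, so separate tabulation is the natural reading, and a new row for cTnI above ULN would largely duplicate an existing one. The AESI definition in 6.5.1 already names both troponins and includes a baseline clause.

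All of this stands. It does not supply the number of participants in each group who reached the CK cut-off. One accepted explanation is the disease state, so attribution can decide which rises are counted. A laboratory-only row gives a comparison that does not depend on it.

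**Conclusion.** The gap is real but minor. Both SAPs plan laboratory-only threshold counts for four kinds of test and none for CK at 5 times the higher of ULN or baseline. The missing comparison matters most in the 52-week SAP, which reports safety by dose group and placebo.

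This is a gap in descriptive reporting. No test or decision rule uses these tables, and nothing here shows that events were missed or that a result is biased. The documents contain no CK, troponin or event counts, so the size of any undercount cannot be stated; the 4-participant and cTnT examples rest on assumed values. The conclusion also rests on the SAP text alone: both SAPs send table content to separate specifications that are not available here. If those already contain the rows, confirming it closes the point.

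**What to change.** In section 6.5.2 of both SAPs:
- Keep the AESI count as defined in 6.5.1.
- Add, by analysis group, the number and percentage of participants with CK at least 5 times the higher of ULN or baseline, whether or not an adverse event was reported. Use the denominator and period already set for the troponin rows and each SAP's own baseline definition.
- Label this row as broader than the protocol AESI, because it does not apply the judgement that the rise is unexplained.
- State that cTnI and cTnT are tabulated separately, and add one cTnT row for values above baseline in participants whose baseline was above ULN. No new cTnI row is needed.

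Counting troponin by analyte, the planned rows go from 32 to 32 + 1 + 1 = 34 in each SAP. The central laboratory already measures CK, cTnI and cTnT (protocol Table 1, footnote g), so no new data are needed. Both SAPs are marked final on 9 July 2024; if they stay closed, the rows can be added and recorded in the clinical study report, where both Introductions send changes of plan. The cost is a little extra tabulation and a CK count that includes explainable rises, which is why the label is needed. The change affects tabulation only and touches no rule for managing participants.
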